11. MEASUREMENT OF EFFECT

11.1 Antitumor Effect – Solid Tumors

For the purposes of this study, patients should be re-evaluated for response every 9 weeks.

Response and progression will be evaluated in this study using the new international criteria proposed by the revised Response Evaluation Criteria in Solid Tumors (RECIST) guideline (version 1.1) [[Eisenhauer 2009](#)]. Changes in the largest diameter (unidimensional measurement) of the tumor lesions and the shortest diameter in the case of malignant lymph nodes are used in the RECIST criteria.

This study will also evaluate response and progression using immune-related response criteria (irRC) [[Wolchok 2009](#)]. See [Appendix C](#) for a detailed description of the evaluation criteria.

11.1.1 *Definitions*

Evaluable for toxicity. All patients will be evaluable for toxicity from the time of their first treatment with atezolizumab and/or CYT107.

Evaluable for objective response. Only those patients who have measurable disease present at baseline, have received at least one cycle of therapy, and have had their disease re-evaluated will be considered evaluable for response. These patients will have their response classified according to the definitions stated below. (Note: Patients who exhibit objective disease progression before the end of cycle 1 will also be considered evaluable.)

Evaluable Non-Target Disease Response. Patients who have lesions present at baseline that are evaluable but do not meet the definitions of measurable disease, have received at least one cycle of therapy, and have had their disease re-evaluated will be considered evaluable for non-target disease. The response assessment is based on the presence, absence, or unequivocal progression of the lesions.

11.1.2 *Disease Parameters*

Measurable disease. Measurable lesions are defined as those that can be accurately measured in at least one dimension (longest diameter to be recorded) as ≥ 20 mm (≥ 2 cm) by chest x-ray or as ≥ 10 mm (≥ 1 cm) with CT scan, MRI, or calipers by clinical exam. All tumor measurements must be recorded in millimeters (or decimal fractions of centimeters).

Note: Tumor lesions that are situated in a previously irradiated area might or might not be considered measurable.

Malignant lymph nodes. To be considered pathologically enlarged and measurable, a lymph node must be ≥ 15 mm (≥ 1.5 cm) in short axis when assessed by CT scan (CT scan slice thickness recommended to be no greater than 5 mm [0.5 cm]). At baseline and in follow-up, only the short axis will be measured and followed.

Non-measurable disease. All other lesions (or sites of disease), including small lesions (longest diameter <10 mm [<1 cm] or pathological lymph nodes with ≥ 10 to <15 mm [≥ 1 to <1.5 cm] short axis), are considered non-measurable disease. Bone lesions, leptomeningeal disease, ascites, pleural/pericardial effusions, lymphangitis cutis/pulmonitis, inflammatory breast disease, and abdominal masses (not followed by CT or MRI), are considered as non-measurable.

Note: Cystic lesions that meet the criteria for radiographically defined simple cysts should not be considered as malignant lesions (neither measurable nor non-measurable) since they are, by definition, simple cysts.

‘Cystic lesions’ thought to represent cystic metastases can be considered as measurable lesions, if they meet the definition of measurability described above. However, if noncystic lesions are present in the same patient, these are preferred for selection as target lesions.

Target lesions. All measurable lesions up to a maximum of 2 lesions per organ and 5 lesions in total, representative of all involved organs, should be identified as **target lesions** and recorded and measured at baseline. Target lesions should be selected on the basis of their size (lesions with the longest diameter), be representative of all involved organs, but in addition should be those that lend themselves to reproducible repeated measurements. It may be the case that, on occasion, the largest lesion does not lend itself to reproducible measurement in which circumstance the next largest lesion which can be measured reproducibly should be selected. A sum of the diameters (longest for nonnodal lesions, short axis for nodal lesions) for all target lesions will be calculated and reported as the baseline sum diameters. If lymph nodes are to be included in the sum, then only the short axis is added into the sum. The baseline sum diameters will be used as reference to further characterize any objective tumor regression in the measurable dimension of the disease.

Non-target lesions. All other lesions (or sites of disease) including any measurable lesions over and above the 5 target lesions should be identified as **non-target lesions** and should also be recorded at baseline. Measurements of these lesions are not required, but the presence, absence, or in rare cases unequivocal progression of each should be noted throughout follow-up.

11.1.3 Methods for Evaluation of Measurable Disease

All measurements should be taken and recorded in metric notation using a ruler or calipers. All baseline evaluations should be performed as closely as possible to the beginning of treatment and never more than 4 weeks before the beginning of the treatment.

The same method of assessment and the same technique should be used to characterize each identified and reported lesion at baseline and during follow-up. Imaging-based evaluation is preferred to evaluation by clinical examination unless the lesion(s) being followed cannot be imaged but are assessable by clinical exam.

Clinical lesions Clinical lesions will only be considered measurable when they are superficial (*e.g.*, skin nodules and palpable lymph nodes) and ≥ 10 mm (≥ 1 cm) diameter as assessed using calipers (*e.g.*, skin nodules). In the case of skin lesions, documentation by color photography, including a ruler to estimate the size of the lesion, is recommended.

Chest x-ray Lesions on chest x-ray are acceptable as measurable lesions when they are clearly defined and surrounded by aerated lung. However, CT is preferable.

Conventional CT and MRI This guideline has defined measurability of lesions on CT scan based on the assumption that CT slice thickness is 5 mm (0.5 cm) or less. If CT scans have slice thickness greater than 5 mm (0.5 cm), the minimum size for a measurable lesion should be twice the slice thickness. MRI is also acceptable in certain situations (*e.g.*, for body scans).

Use of MRI remains a complex issue. MRI has excellent contrast, spatial, and temporal resolution; however, there are many image acquisition variables involved in MRI, which greatly impact image quality, lesion conspicuity, and measurement. Furthermore, the availability of MRI is variable globally. As with CT, if an MRI is performed, the technical specifications of the scanning sequences used should be optimized for the evaluation of the type and site of disease. Furthermore, as with CT, the modality used at follow-up should be the same as was used at baseline and the lesions should be measured/assessed on the same pulse sequence. It is beyond the scope of the RECIST guidelines to prescribe specific MRI pulse sequence parameters for all scanners, body parts, and diseases. Ideally, the same type of scanner should be used and the image acquisition protocol should be followed as closely as possible to prior scans. Body scans should be performed with breath-hold scanning techniques, if possible.

PET-CT At present, the low dose or attenuation correction CT portion of a combined PET-CT is not always of optimal diagnostic CT quality for use with RECIST measurements. However, if the site can document that the CT performed as part of a PET-CT is of identical diagnostic quality to a diagnostic CT (with IV and oral contrast), then the CT portion of the PET-CT can be used for RECIST measurements and can be used interchangeably with conventional CT in accurately measuring cancer lesions over time. Note, however, that the PET portion of the CT introduces additional data which may bias an investigator if it is not routinely or serially performed.

Ultrasound Ultrasound is not useful in assessment of lesion size and should not be used as a method of measurement. Ultrasound examinations cannot be reproduced in their entirety for independent review at a later date and, because they are operator dependent, it cannot be guaranteed that the same technique and measurements will be taken from one assessment to the next. If new lesions are identified by ultrasound in the course of the study, confirmation by CT or MRI is advised. If there is concern about radiation exposure at CT, MRI may be used instead of CT in selected instances.

Endoscopy, Laparoscopy The utilization of these techniques for objective tumor evaluation is not advised. However, such techniques may be useful to confirm complete

pathological response when biopsies are obtained or to determine relapse in trials where recurrence after CR or surgical resection is an endpoint.

Tumor markers Tumor markers alone cannot be used to assess response. If markers are initially above the upper normal limit, they must normalize for a patient to be considered in complete clinical response. Specific guidelines for both CA-125 response (in recurrent ovarian cancer)[[Rustin 2004](#)] and PSA response (in recurrent prostate cancer) [[Bubley 1999](#); [Scher 2008](#)] have been published. In addition, the Gynecologic Cancer Intergroup has developed CA-125 progression criteria which are to be integrated with objective tumor assessment for use in first-line trials in ovarian cancer [[Vergote 2000](#)].

Cytology, Histology These techniques can be used to differentiate between PR and CR in rare cases (e.g., residual lesions in tumor types, such as germ cell tumors, where known residual benign tumors can remain).

The cytological confirmation of the neoplastic origin of any effusion that appears or worsens during treatment when the measurable tumor has met criteria for response or stable disease is mandatory to differentiate between response or stable disease (an effusion may be a side effect of the treatment) and PD.

FDG-PET While FDG-PET response assessments need additional study, it is sometimes reasonable to incorporate the use of FDG-PET scanning to complement CT scanning in assessment of progression (particularly possible 'new' disease). New lesions on the basis of FDG-PET imaging can be identified according to the following algorithm:

- a. Negative FDG-PET at baseline, with a positive FDG-PET at follow-up is a sign of PD based on a new lesion.
- b. No FDG-PET at baseline and a positive FDG-PET at follow-up: If the positive FDG-PET at follow-up corresponds to a new site of disease confirmed by CT, this is PD. If the positive FDG-PET at follow-up is not confirmed as a new site of disease on CT, additional follow-up CT scans are needed to determine if there is truly progression occurring at that site (if so, the date of PD will be the date of the initial abnormal FDG-PET scan). If the positive FDG-PET at follow-up corresponds to a pre-existing site of disease on CT that is not progressing on the basis of the anatomic images, this is not PD.
- c. FDG-PET may be used to upgrade a response to a CR in a manner similar to a biopsy in cases where a residual radiographic abnormality is thought to represent fibrosis or scarring. The use of FDG-PET in this circumstance should be prospectively described in the protocol and supported by disease-specific medical literature for the indication. However, it must be acknowledged that both approaches may lead to false positive CR due to limitations of FDG-PET and biopsy resolution/sensitivity.

Note: A 'positive' FDG-PET scan lesion means one which is FDG avid with an uptake greater than twice that of the surrounding tissue on the attenuation corrected image.

11.1.4 Response Criteria

11.1.4.1 *Evaluation of Target Lesions*

Complete Response (CR): Disappearance of all target lesions. Any pathological lymph nodes (whether target or non-target) must have reduction in short axis to <10 mm (<1 cm).

Partial Response (PR): At least a 30% decrease in the sum of the diameters of target lesions, taking as reference the baseline sum diameters.

Progressive Disease (PD): At least a 20% increase in the sum of the diameters of target lesions, taking as reference the smallest sum on study (this includes the baseline sum if that is the smallest on study). In addition to the relative increase of 20%, the sum must also demonstrate an absolute increase of at least 5 mm (0.5 cm). (Note: the appearance of one or more new lesions is also considered progressions).

Stable Disease (SD): Neither sufficient shrinkage to qualify for PR nor sufficient increase to qualify for PD, taking as reference the smallest sum diameters while on study.

11.1.4.2 *Evaluation of Non-Target Lesions*

Complete Response (CR): Disappearance of all non-target lesions and normalization of tumor marker level. All lymph nodes must be non-pathological in size (<10 mm [<1 cm] short axis).

Note: If tumor markers are initially above the upper normal limit, they must normalize for a patient to be considered in complete clinical response.

Non-CR/Non-PD: Persistence of one or more non-target lesion(s) and/or maintenance of tumor marker level above the normal limits.

Progressive Disease (PD): Appearance of one or more new lesions and/or *unequivocal progression* of existing non-target lesions. *Unequivocal progression* should not normally trump target lesion status. It must be representative of overall disease status change, not a single lesion increase.

Although a clear progression of “non-target” lesions only is exceptional, the opinion of the treating physician should prevail in such circumstances, and the progression status should be confirmed at a later time by the review panel (or PI).

11.1.4.3 *Evaluation of Best Overall Response*

The best overall response is the best response recorded from the start of the treatment until disease progression/recurrence (taking as reference for progressive disease the smallest measurements recorded since the treatment started). The patient's best response assignment will depend on the achievement of both measurement and confirmation criteria.

For Patients with Measurable Disease (i.e., Target Disease)

Target Lesions	Non-Target Lesions	New Lesions	Overall Response	Best Overall Response when Confirmation is Required*
CR	CR	No	CR	>4 wks. Confirmation**
CR	Non-CR/Non-PD	No	PR	>4 wks. Confirmation**
CR	Not evaluated	No	PR	
PR	Non-CR/Non-PD/not evaluated	No	PR	
SD	Non-CR/Non-PD/not evaluated	No	SD	Documented at least once >4 wks. from baseline**
PD	Any	Yes or No	PD	no prior SD, PR, or CR
Any	PD***	Yes or No	PD	
Any	Any	Yes	PD	

See RECIST 1.1 manuscript for further details on what is evidence of a new lesion.
 ** Only for non-randomized trials with response as primary endpoint.
 *** In exceptional circumstances, unequivocal progression in non-target lesions may be accepted as disease progression.
 Note: Patients with a global deterioration of health status requiring discontinuation of treatment without objective evidence of disease progression at that time should be reported as “symptomatic deterioration.” Every effort should be made to document the objective progression even after discontinuation of treatment.

For Patients with Non-Measurable Disease (i.e., Non-Target Disease)

Non-Target Lesions	New Lesions	Overall Response
CR	No	CR
Non-CR/non-PD	No	Non-CR/non-PD*
Not all evaluated	No	not evaluated
Unequivocal PD	Yes or No	PD
Any	Yes	PD

‘Non-CR/non-PD’ is preferred over ‘stable disease’ for non-target disease since SD is increasingly used as an endpoint for assessment of efficacy in some trials so to assign this category when no lesions can be measured is not advised

11.1.5 Duration of Response

Duration of overall response: The duration of overall response is measured from the time measurement criteria are met for CR or PR (whichever is first recorded) until the first date that recurrent or progressive disease is objectively documented (taking as reference for progressive disease the smallest measurements recorded since the treatment started).

The duration of overall CR is measured from the time measurement criteria are first met for CR until the first date that progressive disease is objectively documented.

Duration of stable disease: SD is measured from the start of the treatment until the criteria for progression are met, taking as reference the smallest measurements recorded since the treatment started, including the baseline measurements.

11.1.6 Progression-Free Survival

PFS is defined as the duration of time from start of treatment to time of progression or death, whichever occurs first.

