4.5 General Guidelines

After registration, patients should begin protocol treatment within 5 business days. Issues that would cause treatment delays should be discussed with the PI. If a patient does not receive protocol therapy after registration, the patient's registration on the study may be canceled. The Clinical Research Site (CRS) must notify the CITN Coordinating Center of cancellations as soon as possible.

Except in very unusual circumstances, each participating institution will order DCTD-supplied agents directly from CTEP.

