5. TREATMENT PLAN

This is a phase II trial of atezolizumab (MPDL3280A) plus recombinant human IL-7 (CYT107) in patients with locally advanced or metastatic urothelial carcinoma. The trial follows a randomized, controlled trial design, with an initial 'Safety Run-In' phase designed to evaluate the acute safety profile of the investigational treatment combination.

During the Safety Run-In phase, 6 patients will be assigned to the experimental arm (atezolizumab + CYT107) with staggered enrollment. This will be accomplished with an initial 3 patient enrollment. All adverse events will be assessed by the Toxicity Evaluation Committee. If 0-1 patient experiences a protocol-defined DLT (refer to [Section 5.2](#)) after completion of the 4-week DLT window, an additional 3 patients will be enrolled. Once all 6 patients have completed the 4-week DLT window, the Toxicity Evaluation Committee will again assess all adverse events. If, at any time, 2 or more patients experience a protocol-defined DLT, further enrollment into the trial will be suspended.

If the treatment combination of the experimental arm demonstrates an acceptable safety profile in the Safety Run-In (one or fewer patient experiences a protocol-defined DLT), randomized enrollment into the trial will begin.

Patients will be randomly assigned to either the control arm (atezolizumab monotherapy) or experimental arm (atezolizumab + CYT107) of the trial.

The first 6 subjects enrolled in the run-in phase of the study will have PK sampling done at baseline (prior to CYT107 administration), and at week 4 prior to CYT107 administration and at 2 hours, 4 hours and 6 hours after the fourth CYT107 administration.

Anti-drug antibody testing (ADA testing) will be done on all subjects who receive CYT107. Testing will be done at baseline (prior to CYT107 administration) and at week 8, (1 month after

the last CYT107 administration.) Any subject who develops binding antibodies will be further tested for the presence of anti-CYT107 neutralizing antibodies.

Randomization in the OPEN system may be performed up to 5 business days before initiation of study treatment to allow for clinical site logistics.

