13.3 Sample Size/Accrual Rate

During the Safety Run-In phase, 6 patients will be assigned to the experimental arm (atezolizumab + CYT107) with staggered enrollment (refer to [Section 5](#) for details). The AEs will be assessed by the Toxicity Evaluation Committee. If, at any time, 2 or more patients experience a protocol-defined DLT (refer to [Section 5.2](#)), further enrollment into the trial will be suspended.

If the treatment combination of the experimental arm demonstrates an acceptable safety profile in the Safety Run-In (1 or fewer patient experiences a protocol-defined DLT), randomized enrollment into the trial will begin.

A total of 54 patients will be enrolled in this study; 6 patients in the Safety Run-In and 48 patients in the randomized portion of the study. The expected accrual is 4 patients per month total at approximately 8 CITN sites. A study with 48 randomly assigned patients (1:1 randomization) will meet the following statistical parameters: $H_{\text{null}} = 14.8\%$; $H_{\text{alt}} = 45\%$; one-sided alpha of 0.10; power 88%.

The interim futility analysis will be conducted when 24 randomized patients have their first disease assessment and survival information. The futility analysis is based on an O'Brien-Fleming boundary, and the futility boundary will be considered to be crossed when the difference of ORR in the experimental arm – ORR in the control arm is less than -0.0063. Under the null hypothesis, the probability of crossing the futility boundary is 48.2%.

Safety Population: All patients who receive at least 1 dose of the investigational regimen will be considered evaluable for safety and included in the overall safety analysis. For the Safety Run-in phase, in the absence of a DLT, patients must complete the full 28-day DLT window period to be considered evaluable for DLTs. Patients who discontinue from the study before the completion of the full 28-day DLT window for reasons other than the occurrence of a DLT (e.g., withdrawal of consent, rapid tumor progression, death due to rapid tumor progression, AE that does not meet DLT criteria) will not be considered evaluable for DLTs and will be replaced.

Efficacy Population: The efficacy analysis will be conducted on all randomized patients, based upon the intent-to-treat population.

PLANNED ENROLLMENT REPORT

Racial Categories	Ethnic Categories		Totals
	Not Hispanic or Latino	Hispanic or Latino	

	Female	Male	Female	Male	
American Indian/ Alaska Native	1	2			3

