13.5 Analysis of Secondary Endpoints

13.5.1 Secondary Objectives

Statistical analyses will be conducted for the following secondary objectives:

- The CBR, PFS, DOR, as measured by RECIST v1.1 and irRC, and OS.
- The CBR, PFS, DOR, and OS in patients stratified by PD-L1 expression levels in the tumor microenvironment, as assayed by Genentech.

The CBR is defined as the percentage of patients with advanced or metastatic cancer who have achieved CR, PR, and SD to a therapeutic intervention in clinical trials of anticancer agents. A two-sided test for a difference in proportions will be conducted to compare the CBR in the experimental arm to the CBR in the control arm. A two-sided significance level of 0.05 will be considered for the test.

The PFS, DOR, and OS will be summarized using Kaplan-Meier estimates. Long-rank tests will be conducted for OS and PFS to compare between the 2 arms. A one-sided significance level of 0.10 will be considered.

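### PFS is timed from the start of treatment, so a randomized patient who is never dosed has no PFS time in a comparison meant to cover all randomized patients

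*Combined protocol and SAP*

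**What the plan says.** The combined protocol and SAP defines PFS once, in section 11.1.6: "PFS is defined as the duration of time from start of treatment to time of progression or death, whichever occurs first".

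The analysis set is in section 13.3, under Efficacy Population: "The efficacy analysis will be conducted on all randomized patients, based upon the intent-to-treat population". The PFS comparison is in section 13.5.1: "Long-rank tests will be conducted for OS and PFS to compare between the 2 arms". The level follows: "A one-sided significance level of 0.10 will be considered".

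Two other sections separate randomization from first dose. Section 5 states: "Randomization in the OPEN system may be performed up to 5 business days before initiation of study treatment to allow for clinical site logistics". Section 4.5 adds: "If a patient does not receive protocol therapy after registration, the patient's registration on the study may be canceled".

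Section 13.6.2 says the main response-rate analysis may leave out patients who were given no study drug. The opening of section 13 says there will be no separate SAP, so this protocol is the only place where the rule can be stated.

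**The concern.** A log-rank test needs a time and an event indicator for every patient in it. The definition supplies a time only for patients who start treatment, while the declared population is everyone randomized. For a randomized patient who is never dosed, the two statements cannot both be applied. Following the definition literally means leaving that patient out.

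The trial is open-label (section 2.1; the study summary lists no blinding), so a patient can decline after learning the assigned arm. Patients who never start need not be balanced between arms, and removing them weakens the protection that randomization gives. The protocol applies the same principle in section 13.2, where it keeps the six non-randomized run-in patients out of the main analysis so that they do not bias randomized comparisons.

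**Working it through.** The point rests on definitions, so the main check is to follow patients through the text. The arithmetic only sizes it.

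**1. Patients under the current wording**

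| Patient | Start of treatment | PFS time (11.1.6) | In the efficacy set (13.3) |
|---|---|---|---|
| Randomized and dosed | Yes | Defined | Yes |
| Randomized, never dosed | None | Undefined | Yes |
| Run-in, dosed | Yes | Defined | No, reported separately (13.2) |

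Only the second row conflicts. I looked for a rule that resolves it:
- Section 5.6 (follow-up) is written largely around discontinuation of study treatment.
- Section 5.7 (replacement) covers run-in patients who leave before the end of the DLT window.
- Section 13.6.2 (response) permits leaving undosed patients out.
- No section gives a substitute origin or a censoring rule for PFS.

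**2. Weight of one patient**

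Section 13.3 gives 48 randomized patients at 1:1, so 48/2 = 24 per arm. One undosed patient is 1/24 = 4.2% of an arm and 1/48 = 2.1% of the randomized set.

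**3. Shift for treated patients**

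Five business days span at most one weekend, so about 5 + 2 = 7 calendar days (public holidays aside). Imaging is every 9 ± 1 weeks (section 10), or about 63 days. The window is the same in both arms.

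**4. The plan's own power figure**

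The only power stated for a between-arm comparison is 88% for ORR (14.8% against 45%, 24 per arm, one-sided 0.10). With unpooled variance:

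- SE = √[(0.148×0.852 + 0.45×0.55)/24] = 0.1248
- Power = Φ(0.302/0.1248 − 1.2816) = 87.3%

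The pooled-variance version gives 85.6%. The unpooled figure is close to the stated 88%. The PFS origin does not enter this calculation, so moving it changes no stated figure.

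**5. Illustrative effect on the PFS test**

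The documents give no PFS hazard ratio, event count or power. I assume that all patients in the test have an event, hazard ratios of 0.5 to 0.7, and one-sided 0.10. Schoenfeld's formula is Φ(√(E·p·(1−p))·|ln HR| − 1.2816), where E is the number of events and p the share of patients in one arm.

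| Patients in test | HR 0.5 | HR 0.6 | HR 0.7 |
|---|---|---|---|
| 48 (24 + 24) | 86.9% | 68.7% | 48.2% |
| 47 (one lost from one arm) | 86.3% | 68.0% | 47.6% |
| 44 (four lost from one arm) | 84.3% | 65.8% | 45.9% |

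Losing four patients costs 2.6, 2.9 and 2.3 points, or about 0.6 to 0.7 points per patient. Power is therefore not the main issue. Comparability of the arms is.

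**The case against.** The strongest reply is that no sentence says undosed patients leave the PFS test. Section 13.3 says the reverse, and an analyst might use randomization as a substitute origin. A reader might infer that the plan abandons intent-to-treat for PFS, and the documents do not support that. What stands is that the definition gives these patients no time, and any convention that keeps them is unstated.

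A reader might also take section 4.5 as a forecast of non-starters. It is conditional and gives no rate, and the same section asks for treatment to begin within 5 business days. The number could be zero.

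Nor is PFS in treated patients materially distorted. No on-study scan is scheduled in the short gap before dosing, eligibility requires a life expectancy of at least 12 weeks (section 3.1.6), and both arms have the same window. That objection stands in full.

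PFS is a secondary endpoint, and the trial is sized on ORR. That also stands, and it limits the importance of the point.

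Finally, a new origin alone may recover nothing. If registration is cancelled and follow-up stops, the patient is censored at time zero and contributes nothing to the log-rank test. This is correct, and the fix has to cover follow-up as well.

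**Conclusion.** The point holds in a limited form. The only PFS definition conflicts with the declared analysis population for any randomized patient who is never dosed, and no other section resolves it. Applied literally, it is a post-randomization exclusion in an open-label trial, at 4.2% of an arm per patient.

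The size depends on a count that the documents do not project and that may be zero. That exclusions would differ by arm is a plausible inference from the open-label design, not something the documents show. The power losses shown rest on assumed hazard ratios and events in all patients.

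Two stronger readings should be avoided. The ORR power and sample size are not affected by the PFS origin. OS is not timed from the wrong date, because the documents give no OS origin at all; stating one is a clarification.

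**What to change.** 1. In section 11.1.6, define PFS from the date of randomization for the 48 randomized patients. Keep start of treatment for the 6 run-in patients, who are reported separately.
2. State that randomized patients who are never dosed remain in the PFS and OS analyses. Follow disease status and survival where consent allows, and otherwise censor at last contact.
3. Reconcile the cancellation wording in section 4.5 with section 13.3, so that cancelling a registration does not remove a randomized patient from the efficacy analysis or end follow-up.
4. Reconcile the exception for undosed patients in section 13.6.2 with section 13.3.
5. State randomization as the OS origin in the randomized comparison, for clarity only.

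The cost is a short text amendment across these sections and limited follow-up of any undosed patients. Randomization runs through OPEN, so its date should already be recorded. Sample size and stated power are unchanged.
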